All interested potential participants (PSW's and other support workers in long-term care and retirement homes) will receive a link to the pre-screening survey (Appendix C) to determine eligibility. If eligible, participants will receive a pre-screening confirmation email (Appendix D) which will contain the link to the study information sheet and informed consent process (Appendix E). Contact information for members of the study team will also be provided. Participants will be encouraged to reach out with any questions. Participants will be asked to review all the study details and provide consent by selecting one of the two consenting statements at the end of the survey. Participants will then be emailed their unique study ID and the link to the baseline survey. The study team will reach out again at 6 months with a link to complete an exit survey.

Consent at enrollment includes participating in:

- 1:1 sessions with the resource navigator and access to educational resources (if assigned to intervention arm. Access to educational resources only (if assigned to the control arm)
- Participation in the baseline survey and exit survey. Participants will be assigned to either an intervention or control arm and will be invited by email (Appendix F - initial email, G - reminder email) to complete the baseline survey, a demographic questionnaire (Appendix H). The baseline survey will be used to select a diverse participant group (purposive sample). Participants will be given the opportunity to consent and provide their OHIP number for data linkage. An invitation email (Appendix I – initial email, J – reminder email) will also be sent to complete the exit survey (Appendix K) where they will also be given the opportunity to provide their OHIP number for data linkage if not provided during the baseline survey.
- Participants' response to any questionnaire will be kept confidential. Participants will be provided with a unique study ID (Appendix F, I) to complete the baseline and exit survey

Evaluating the impact of resource navigators to support long-term care and retirement home staff during and beyond COVID-19

Principal Investigators: Drs. [name] and [name]

Research ethics protocol

Version Dates: Sept 7th, 2022

Version Number: 2

(Appendix H, K) so that their responses remain de-identified. Identifiers and unique study IDs will be recorded on a master linking log (Appendix L).

At 6 months, we will select and invite 10 participants from the intervention arm and 10 participants from the control arm to take part in a brief key informant interview (mentioned above as an exit interview). We will purposefully sample participants for diversity in role, race/ethnicity, and age. Participants will coordinate with a research staff member for a date/time that works best and also identify their preferred form of communication (Appendix M). Participants will be provided with a reminder email (Appendix N) 2 business days prior to the interview date/time.

Verbal consent will be obtained prior to the start of the interview by the interviewer using a pre-determined script (Appendix O, P) and participants will be given the opportunity have any questions answered. Verbal consent will be captured and recorded once the audio recorder is turned on. Participants will only be identified by participant IDs in the consent recording. Consent to participate will also be recorded on the master linking log (Appendix L). Participants are free to skip questions and/or withdraw from the study.

As an incentive to complete the study surveys, all participants will receive a \$20 gift card upon completion of each survey (\$20 gift card per survey x 2 surveys = \$40 gift card). Participants that complete the interview will also receive a \$50 gift card.

27. Confidentiality

All study-related information will be stored on a secure server. In accordance with all applicable privacy legislation, including the *Personal Health Information Protection Act* (PHIPA) of Ontario, Canada, participant personal information will be kept private and confidential.

Participant data will be de-identified using a participant ID and stored on Unity Health's secure server. Identifiers and unique study IDs will be recorded on a master linking log (Appendix L). All study information will be stored according to the process described above until 7 years after the end of the study, after which it will be securely destroyed.

28. Declaration Of Interests

There are no competing interests or conflicts of interest to declare.

29. Access to Data

All participant who complete the baseline survey, intervention and exit survey will be requested to link their study data to their OHIP number. Only the study team will have access to the identifying personal information collected for this study.

Evaluating the impact of resource navigators to support long-term care and retirement home staff during and beyond COVID-19

Principal Investigators: Drs. [name] and [name]

Research ethics protocol

Version Dates: Sept 7th, 2022

Version Number: 2

30. Ancillary and Post-Trial Care

Ancillary and post-trial care are not applicable for this study.

31. Dissemination Policy

31a. Trial Results

We will use the CIHR End of Grant (EoG) framework to guide EoG dissemination activities tailored to each end user.[48] We will publish our findings in open-access peer reviewed journals, and alongside OPSWA, will present at relevant national conferences. We will use various active and passive strategies to disseminate the findings to knowledge users, including our >20 collaborators via the CITF-funded study including the OLTCA, FCO, Toronto and Ottawa LHINs, Ministries of Health and of LTC, Public Health Agency of Canada, Public Health Ontario, and Healthcare Excellence Canada.[49] We will report the study results using the relevant reporting guidelines including the Consolidated Standards of Reporting Trials (CONSORT) statement, the Template for Intervention Description and Replication (TIDieR) checklist, and the Sex and Gender Equity in Research (SAGER) guidelines.[29, 50-51]

31b. Authorship

We will use the International Committee of Medical Journal Editors (ICMJE) criteria for authorship and no professional writers will be used.

31c. Reproducible Research

As per the funder's guidelines, the study team will make data available after the study has been submitted. The study protocol will also be registered and available via clinicaltrials.gov.

Appendices

32. Informed consent materials

Evaluating the impact of resource navigators to support long-term care and retirement home staff during and beyond COVID-19

Principal Investigators: Drs. [name] and [name]

Research ethics protocol

Version Dates: Sept 7th, 2022

Version Number: 2

Timeline

Milestone Tasks	Project Month					
	June-July 2022	Aug-Sep 2022	Oct-Nov 2022	Dec 2022 – Feb 2023	March-April 2023	May – June 2023
Assign participants to intervention arm	X					
Baseline survey	X					
Conduct intervention		X	X	X		
Process evaluation tracking		X	X	X		
Exit survey					X	
Conduct exit interviews					X	
Analyze data					X	X
Write final report						X

Evaluating the impact of resource navigators to support long-term care and retirement home staff during and beyond COVID-19

Principal Investigators: Drs. [name] and [name]

Research ethics protocol

Version Dates: Sept 7th, 2022

Version Number: 2

Budget

Budget Item	Funds requested YEAR 1							
	FTE	hours	Salary	Benefits	Subtotal	In-Kind	Total	Rate
RESEARCH STAFF (excluding trainees)								
Resource Navigator/Officer (RC I)	2.65	5168	\$182,554.13	\$41,987	\$224,542		\$224,542	\$35.33
Research Coordinator II (0.5FTE)	0.50	975	\$38,025.00	\$8,746	\$46,771		\$46,770	\$39.00
Research Assistant I (1.0TE)	1.00	1950	\$52,767.00	\$12,136	\$64,903		\$64,903	\$27.06
Statistician	0.07	133	\$7,559.72	\$1,739	\$9,298		\$9,391	\$56.84
Summer students (x2)	0.17	336	\$6,232.78	\$0	\$6,233		\$6,233	\$18.54
Total personnel							\$351,839	
MATERIALS, SUPPLIES, and SERVICES								
Expendables			quantity	per unit	Subtotal		Total	
Cellphone & data/voice plan (2 phones)			2.00	\$1,626.00	\$3,252		\$3,252	
Jabber line			1.00	\$10/m	\$120		\$120	
Voice recorders			2.00	\$75.00	\$150		\$150	
Printing costs (154 participants x ~\$10/package)					\$3,100		\$3,100	
Services								
REDCap			1.00	\$2,000	\$2,000		\$2,000	
Transcription Services			100	\$33.28	\$3,328		\$3,328	
ICES Services					\$35,000		\$35,000	
Translation Services					\$25,000		\$25,000	
Knowledge Translation and IKT (Other)								
Maslach Burnout Inventory Scale					\$400		\$400	
PSW Partners compensation (\$400/partner/yr CIHR; \$300/part/yr T)			6.00	\$400	\$2,100		\$2,100	
OPSWA Compensation					\$13,750		\$13,750	
Participant Survey Reimbursement (154 p x 2 surveys/ each grant)			616	\$10	\$6,160		\$6,160	
Participant Interview Reimbursement			20.00	\$50	\$1,000		\$1,000	
Manuscript Publication			4.00	\$3,707	\$14,828		\$14,828	
End of Grant dissemination materials					\$3,500		\$3,500	
Total materials					\$113,688		\$113,688	
Travel								
Travel & Presentation at National Conferences					\$2,400		\$2,400	
Total Travel					\$2,400		\$2,400	
EQUIPMENT								
Laptops (Dell Latitude 7400)			3.00	\$3,500	\$10,500		\$10,500	
Audio voice recorders			1.00	\$75	\$75		\$75	
Total equipment					\$10,575		\$10,575	
TOTAL							\$478,502	

Evaluating the impact of resource navigators to support long-term care and retirement home staff during and beyond COVID-19

Principal Investigators: Drs. [name] and [name]

Research ethics protocol

Version Dates: Sept 7th, 2022

Version Number: 2

References

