Participants may be inconvenienced by taking part in components of the study (e.g., exit interviews). The COVID-19 pandemic is also a stressful situation to many; therefore, risks will be mitigated by ensuring participants are aware that they have the option to participate and/or not answer any questions they do not wish to answer. Participants will be able to withdraw from the study at any point with no consequences by notifying a study coordinator, investigator or the resource navigator. Participants may have to withdraw due to end of employment or personal concerns. Preliminary sample size estimations have been calculated to account for participant attrition.

11c. Adherence

To facilitate adherence to the intervention, participants in the intervention arm will receive a package that includes educational resources by email and/or mail each month. Resource navigators will directly reach out to participants in the intervention arm (via email/phone) and will provide them with two hours of navigation support sessions (by phone/zoom) per month for six months. Additionally, during the course of the intervention, the resource navigation will also identify processes to enhance adherence for the six-month period through various methods including personalization of sessions (participant's communication and time preference) and providing ambient information pre-session (session reminders, goal of each session).

11d. Concomitant Care

Due to the nature of this study, all participants will be assessed if they are receiving other interventions related to wellness, which can be self-directed or organization directed. This will also enable the identification co-intervention bias, which can impact on the study outcome

12. Outcome Measures

1. Primary Outcome Measures

The primary outcome for this study is the impact of the intervention on staff wellness. This will be measured by determining the impact of resource navigation on the change in wellness between the 6-month time point and baseline for those who received educational resources and resource navigation compared to those who received educational resources alone.

Participant wellness will be assessed using the Personal Wellbeing Score.[31] The Personal Wellbeing Score measure was selected to align with the World Health Organization's 2004

Evaluating the impact of resource navigators to support long-term care and retirement home staff during and beyond COVID-19

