This study estimates that the standard deviation (SD) across mean Personal Wellbeing Scores is 10.2.[31] Assuming we will use a t-test to compare the scores across the intervention groups, a medium effect size of 0.5, a SD estimate of 10.2, a false positive error rate of 5% and a power of 80%, the estimated sample size is 64 participants per arm or 128 for the two arms. Including a buffer for participation attrition of 20%, the study will require a total of 154 participants (77 per arm).

Evaluating the impact of resource navigators to support long-term care and retirement home staff during and beyond COVID-19

Principal Investigators: Drs. [name] and [name]

Research ethics protocol

Version Dates: Sept 7th, 2022

Version Number: 2

15. Recruitment

The study team will be using multiple recruitment strategies: circle of contacts, snowball, and advertisements (Appendix A, B, Y). The study team will also leverage partnerships with OPSWA, Ontario LTC Association (OLTCA), Family Councils Ontario (FCO), and other Long Term Care and retirement organizations to recruit PSWs and other service support staff working in Ontario long-term care and retirement homes. All interested potential participants will be provided with a pre-screening survey to determine eligibility, the study information sheet and a consent form..

Methods: Assignment of Interventions (for controlled trials)

16. Allocation

16a. Sequence Generation

Participants will be randomly assigned to either control or intervention group with a 1:1 allocation sequence using computer software and will use block randomization with randomly selected block sizes to keep the enrollment sizes in each arm similar throughout the trial. [40] This will be done under the supervision of the study statistician (BP).

16b. Concealment Mechanism

The study team will use a secure web application called Research Electronic Data Capture (REDCap) to randomly allocate participants to the intervention and control arms, which will conceal the sequence and allocation until the point of assignment. [40]

16c. Implementation

All participants who provide consent for participation and who fulfil the inclusion criteria will be randomized. A statistician from the study team will generate the random allocation sequence. Research coordinators of the study will enroll participants and assign them to a study arm (control or intervention arm).

17. Blinding

17a. Blinding (Masking)

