We will use descriptive statistics to report participant demographics and study outcomes. We will use t-tests to compare outcomes for the intervention and control groups. We will disaggregate data by sex, gender, age, long-term and retirement home staff type, and long-term care home type (e.g., for-profit, municipally owned). Where possible (for cells with $n \geq 5$), we will disaggregate data by other PROGRESS-Plus demographics, in line with an intersectionality-based approach. [31, 37, 44-45, 48].

20b. Additional Analysis

There is no additional analysis that has been identified for this research study.

20c. Analysis Population and Missing Data

Evaluating the impact of resource navigators to support long-term care and retirement home staff during and beyond COVID-19

Principal Investigators: Drs. [name] and [name]

Research ethics protocol

Version Dates: Sept 7th, 2022

Version Number: 2

The analysis of the population, as earlier identified, includes a t-test for the comparison of both the control and intervention groups, and also qualitative analysis with the use of NVivo. All questions are optional and participants can skip questions they do not feel comfortable answering. We will consult with a study statistician to develop a plan for missing data.

Methods: Monitoring

21. Data Monitoring

21a. Formal Committee & (b) Interim Analysis

Due to the length and minimal risks associated with the study, a Data Monitoring Committee and interim analysis will not be required. Data will be monitored throughout the duration of the study by the Research Coordinator and Research Assistant in accordance with the Unity Health Toronto Institutional Review Board guidance and standards. The Research Ethics Board may request to review the study records for monitoring purposes.

22. Harms

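### The plan does not commit to comparing everyone as randomised, and its default t-test on complete baseline–exit pairs is inefficient and can be biased

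*Combined protocol and SAP*

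**What the plan says.** **Contrast.** Section 12 (Primary Outcome Measures) takes "the change in wellness between the 6-month time point and baseline" as the endpoint and compares it "for those who received educational resources and resource navigation compared to those who received educational resources alone".

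**Groups.** Section 16a: "Participants will be randomly assigned to either control or intervention group with a 1:1 allocation sequence". Section 20a: "We will use t-tests to compare outcomes for the intervention and control groups".

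**Analysis set and missing data.** Section 20c carries both topics in its title, but its text on the first is "The analysis of the population, as earlier identified, includes a t-test for the comparison of both the control and intervention groups", followed by a mention of the qualitative analysis. On the second it says "We will consult with a study statistician to develop a plan for missing data". Section 20b plans no further analyses.

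**Routes to missing scores.** Baseline is collected 0–30 days after randomisation (Section 13). Every question may be skipped (20c). Data can be withdrawn until analysis starts (22). Section 11b expects some loss: "Participants may have to withdraw due to end of employment or personal concerns". Section 14 allows for 20% attrition.

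**Linkage.** Section 29: "All participant who complete the baseline survey, intervention and exit survey will be requested to link their study data to their OHIP number". Section 26a offers linkage at the baseline survey and again at exit, and Table 1 lists it for up to 154 participants.

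**The concern.** Two analysts could follow this text and report different primary results. One would analyse all participants in their assigned arm. The other could take Section 12 literally and treat someone assigned to navigation who attends none of the 12 sessions as having received resources alone, either dropping that person or counting them as a control. Attendance is plausibly related to workload and wellness, so the second analysis would compare self-selected groups.

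The missing-data gap is the more practical problem. With no method stated, a t-test on change discards anyone lacking either score. In an open-label trial with a self-reported outcome, the reasons for not returning a survey may differ by arm, and no sensitivity analysis is planned that would show it.

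**Working it through.** **1. The plan's own figure.** Inputs from Section 14: SD 10.2, effect size 0.5 (0.5 × 10.2 = 5.1 points), 5% error rate, 80% power. A two-sided two-sample t-test needs 63.8, so 64 per arm, as stated (power 80.1%). Then 64 × 1.20 = 76.8, so 77 per arm and 154 in total.

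**2. Efficiency of the change t-test.** With baseline–exit correlation r (not given in the protocol; 0.5 assumed):
- SD of change = 10.2 × √(2(1 − r)) = 10.2 × √1 = 10.2.
- Residual SD after baseline adjustment = 10.2 × √(1 − r²) = 10.2 × √0.75 = 8.83.

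At 17% missing, 77 × 0.83 ≈ 64 complete pairs per arm remain. Power for 5.1 points is then 80% (d = 5.1/10.2 = 0.50) against 90% (d = 5.1/8.83 = 0.58). At r = 0.3 the pair is 66% and 84%; at r = 0.7 it is 95% and 98%.

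**3. Dropout that depends on baseline.** For a given baseline, expected change falls by (1 − r) per point. So bias of the change t-test = −(1 − r) × (between-arm difference in mean baseline among completers).

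Assumed scenario, simulated with 8,000 replicates: 77 per arm, r = 0.5, true effect 5.1; control 17% missing at random; navigation log-odds of missing −1.5, minus 1 per baseline SD (about 22% missing). Navigation completers then start about 2 points higher, so bias ≈ −0.5 × 2 = −1.0 point.

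| Missingness | Change t-test: bias, power | Baseline-adjusted: bias, power |
|---|---|---|
| Random, 17% in both arms | about 0, 80% | about 0, 90% |
| Low-baseline staff leave navigation | −1.0, about 60% | about 0, 88% |
| Same selective dropout in both arms | 0, 78% | 0, 88% |

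**4. If receipt were applied literally.** Assumed: no true effect, 64 per arm, SD of change 10.2, and a share p of never-starters whose change is g SD worse. By randomisation, the control arm holds the same share of such people.
- Moved to control: bias = 2pg/(1 + p); SE = √(1/[64(1 − p)] + 1/[64(1 + p)]).
- Excluded: bias = pg; SE = √(1/[64(1 − p)] + 1/64).
- Type I error = Φ(−1.96 + bias/SE) + Φ(−1.96 − bias/SE).

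Example with p = 0.2, g = 0.5, moved: bias = 0.2/1.2 = 0.167 SD = 1.7 points; SE = √(1/51.2 + 1/76.8) = 0.180; ratio 0.924; type I error = 0.150 + 0.002 = 15.2%.

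| p | g | Moved: points | Type I, formula / simulated | Excluded: points | Type I, formula / simulated |
|---|---|---|---|---|---|
| 10% | 0.3 | 0.56 | 6.1% / 6.1% | 0.31 | 5.3% / 5.5% |
| 10% | 0.5 | 0.93 | 8.0% / 7.6% | 0.51 | 5.9% / 5.7% |
| 20% | 0.3 | 1.02 | 8.6% / 8.4% | 0.61 | 6.2% / 5.9% |
| 20% | 0.5 | 1.70 | 15.2% / 14.6% | 1.02 | 8.3% / 8.4% |
| 30% | 0.3 | 1.41 | 11.6% / 11.5% | 0.92 | 7.5% / 7.5% |
| 30% | 0.5 | 2.35 | 23.8% / 22.1% | 1.53 | 12.0% / 11.4% |

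Simulated values use 40,000 replicates. The formula runs slightly high because it ignores the extra spread from mixing the two kinds of participant. Analysis as randomised stays at about 5% throughout.

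**5. Dropout that depends on the outcome itself.** Assumed: no true effect, 20% missing in each arm, random in control, and navigation non-completers worse than completers by 0.25–1.0 SD. Bias = 0.20 × (0.25 to 1.0) = 0.05–0.20 SD (0.5–2.0 points), and type I error is 5.9–20%. Baseline adjustment alone does not remove this.

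**The case against.** The strongest reply is that 'received' simply describes the arms. Sections 7 and 11a use the same verb for what each arm is given, and Sections 16a and 20a compare assigned groups. Section 20c's backward reference is to the t-test in 20a, not to the wording in Section 12. No passage sets a minimum number of sessions or moves anyone between arms. Section 17a keeps the outcome analysts blind to assignment, and Table 1 plans session logs for 77 participants only, so regrouping by attendance would tend to unblind them. All of this stands. A reader might infer that the plan lays down a by-receipt rule; the documents do not support that. Nor do they state a restriction to people with both surveys, which is only what the named test does when no other method is given.

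A reader might also infer from Section 29 that only completers are linked. Section 26a and Table 1 show otherwise, and linkage supplies secondary outcomes only. This is a wording mismatch.

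The gap between 80% and 90% power is covariate efficiency at an assumed correlation, not repair of missing-data bias, and the bias in step 3 runs against navigation.

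Finally, baseline can follow the start of navigation, so a common baseline mean is not guaranteed. That is a real limit on the remedy, but it does not favour the t-test. If navigation had already raised baseline by 0.2 SD (2.04 points, assumed), the change t-test would lose all 2.04 points and the adjusted model 0.5 × 2.04 = 1.02.

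**Conclusion.** The concern holds as a failure to secure the randomised comparison. Section 12 conflicts in wording with Sections 16a and 20a, and Section 20c settles neither the analysis set nor the handling of missing scores. The documents do not show that randomisation will in fact be broken.

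The firmest cost is efficiency: about 10 percentage points of power at r = 0.5, more at a lower correlation and less at a higher one. Bias from complete pairs is conditional: about −1.0 point, a fifth of the 5.1-point target, in the scenario shown, and none if missingness is alike in both arms. The type I error figures for literal receipt apply only if Section 12 were carried out word for word. Never-start rates, dropout patterns and the correlation are all assumptions. The change should be made before arm-level data are seen.

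**What to change.** - **Section 12:** replace 'those who received' with 'those randomised to'.
- **Section 20c:** state that all randomised participants are analysed in their assigned arm, whatever number of sessions they attended.
- **Sections 20a and 20c:** replace the t-test on change with a baseline-adjusted likelihood model of the baseline and 6-month Personal Wellbeing Scores, so that anyone with at least one score contributes. Fix it before arm-level data are seen.
- **Sensitivity analyses:** add one delta-adjusted analysis for missing exit scores. Add one limited to baselines completed before the first session, because the model's common baseline mean is otherwise not guaranteed.
- **By sessions received:** any such analysis is secondary.
- **Section 29:** align its linkage wording with Section 26a.

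The cost is some protocol wording and slightly more analysis, with no added participants or visits. The as-randomised effect may be smaller than an as-received one.
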